#### 6.5.1.5 Definition of local control

Local control will be defined as sustained stable disease, partial response, or complete response in the target lesion(s) at one year post-treatment.

Local Response Rate is defined as stable disease, partial response, or complete response per RECIST at any point in the first year of follow-up.

Local failure will be defined as any progression of disease within the target volume.

Regional failure will be defined as development of new liver metastases outside of the treated lesions.

Distant failure will be defined as development of new metastatic lesions outside of the liver (brain, bone, etc).

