## Secondary

- 2.2 To evaluate the local control associated with this local regional therapy.
- 2.3 To determine local response based on FDG-PET/CT compared to CT only.
- 2.4 To evaluate the HRQL associated with this therapy

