#### 6.3 Follow up Interval

The patient will be followed post-treatment for 16 months, or until death unless otherwise indicated. Evaluation during the follow up interval will consist of the following activities:

- 6.3.1 Physical exam and vital signs at one, two, and three months post SBRT, five months post SBRT, and then every three months thereafter.
- 6.3.2 Monthly blood work to be done at a local laboratory starting 2 weeks following SBRT CBC, Diff with platelets, basic electrolytes, BUN, creatinine, t-bili, ALT, AST, GGTP, calcium, magnesium, and phosphorus. Bloodwork to be completed for at least the first six months.
- 6.3.3 CT or FDG-PET/CT scans (for consistency procedure done at screening/planning will continue in follow-up) at 8 weeks post-treatment and every 12 weeks thereafter for 12 months for assessment of response to therapy and monitoring.
- 6.3.4 Patients will follow up with their treating medical oncologist after SBRT, and if deemed appropriate, will be able to start systemic therapy 2 weeks after treatment.

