#### 7.3.2 Analysis of Secondary Endpoints

Local control, local failure, regional failure and distant failure of patients, defined in Section 6.5.1.5, will be summarized in tables. Their rate will be calculated along with their exact 95% confidence intervals. The local response rates with FDG-PET/CT will be compared to those with CT using McNemar's test. The HRQL data analysis will be mostly descriptive and performed according to Section 6.5.1.6.

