#### **Confirmation**

- The main goal of confirmation of objective response is to avoid overestimating the response rate observed. In cases where confirmation of response is not feasible, it should be made clear when reporting the outcome of such studies that the responses are not confirmed.
- To be assigned a status of PR or CR, changes in tumor measurements must be confirmed by repeat assessments that should be performed no less than 4 weeks after the criteria for response are first met. Longer intervals as determined by the study protocol may also be appropriate.
- In the case of SD, follow-up measurements must have met the SD criteria at least once after study entry at a minimum interval (in general, not less than 6-8 weeks) that is defined in the study protocol

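### The PET-versus-CT response comparison has no PET definition of response, its CT definition counts stable disease at any one scan, and the CT progression rule differs between two sections

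*Combined protocol and SAP*

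**What the plan says.** Objective 2.3 (section 2.0) is: "To determine local response based on FDG-PET/CT compared to CT only". Section 7.3.2 gives the analysis: "The local response rates with FDG-PET/CT will be compared to those with CT using McNemar's test". The rate is defined once, in 6.5.1.5: "Local Response Rate is defined as stable disease, partial response, or complete response per RECIST at any point in the first year of follow-up". In that same section local control must be sustained and is judged at one year; the response rate carries neither condition.

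Other parts that bear on the comparison:

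- **PET criteria (6.5.1.3).** EORTC 1999 is adopted and four categories are listed: progressive (PMD), stable (SMD), partial response (PMR) and complete response (CMR). They are not divided into responders and non-responders. Non-avid tumours are rated by CT.
- **Purpose (Protocol Summary, Efficacy data collected).** RECIST and EORTC 1999 are both named for objective response. A separate item sets PET/CT against CT for judging local control.
- **Scans (6.3.3).** Imaging takes place "at 8 weeks post-treatment and every 12 weeks thereafter for 12 months", and the modality is fixed: "for consistency procedure done at screening/planning will continue in follow-up".
- **Confirmation (Appendix II).** For PR or CR, "changes in tumor measurements must be confirmed by repeat assessments that should be performed no less than 4 weeks after" the criteria are first met. Stable disease need be met only once after a minimum interval, "in general, not less than 6-8 weeks".
- **Other endpoints (7.3.2).** "Local control, local failure, regional failure and distant failure of patients, defined in Section 6.5.1.5, will be summarized in tables".
- **Status (7.3).** Analyses are declared exploratory because of the small sample.

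**The concern.** McNemar's test needs a yes or no from each modality for the same patient. The plan supplies that on the CT side only. Someone must decide whether SMD counts on PET, and nothing prevents that decision being made after the scans have been read. The same data could then be reported as showing a difference or none.

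The CT definition is also generous. A patient who is stable at the 8-week scan, which can meet Appendix II's general minimum, and who progresses later remains a responder for this endpoint. Stable disease would be reported as response.

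Two faults in the criteria add to this. Section 6.5.1.3 gives no category to an SUV fall of 15% to below 25%. Section 6.5.1.2 and Appendix II disagree on what CT progression is.

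**Working it through.** **Inputs.** The maximum is 18 evaluable patients (7.2), which 3 dose levels x 6 patients = 18 (7.1) reproduces. The plan gives no rate, effect size, significance level, sidedness or version of the test for this comparison. The exact two-sided 5% test and all response rates below are therefore assumptions.

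**1. What the test needs.** With d discordant pairs all in one direction, exact p = 2 x 0.5^d. Five pairs give 0.0625 and six give 0.031, so at least six are needed. The uncorrected chi-square version would need four (p = 0.0455).

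**2. The mapping alone moves the result.** Take one invented set of 18 patients with nested categories: CT 1 PD, 9 SD, 8 PR/CR; PET 1 PMD, 7 SMD, 10 PMR/CMR.

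| Counted as response | CT | PET | Discordant | p |
|---|---|---|---|---|
| Stable counted on both | 17/18 | 17/18 | 0:0 | 1.0 |
| Stable counted on CT only | 17/18 | 10/18 | 7:0 | 0.016 |
| Stable counted on neither | 8/18 | 10/18 | 0:2 | 0.50 |

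**3. Stable disease on both sides.** A CT rate of 95% is plausible. The 71% one-year local control cited in section 1.3, carried back to week 8 at an assumed constant hazard, gives 0.71^(8/52.18) = 0.949. If the modalities are independent, the discordant probabilities are CT x (1 - PET) and PET x (1 - CT). For CT 0.95 and PET 0.85 these are 0.1425 and 0.0425. Exact power with 18 pairs:

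| PET rate | Independent | Nested |
|---|---|---|
| 95% | 0.00014 | 0 |
| 90% | 0.0028 | below 0.0028 |
| 85% | 0.019 | 0.0064 |
| 75% | 0.150 | 0.133 |

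**4. Stable disease on CT only.** Suppose the modalities agree on every patient and a share s is stable on both. Each such patient is discordant by definition, so the chance of a significant result is P(Bin(18, s) >= 6): 0.006 at s = 10%, 0.042 at 15%, 0.133 at 20%, 0.283 at 25%. It passes 5% at s of about 16%.

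**5. Non-avid tumours.** They are rated by CT, so they agree by construction if kept. With k such patients among 18, an assumed 40-point difference in avid tumours shrinks to 40 x (18 - k)/18: 35.6 points for k = 2 and 26.7 for k = 6.

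**6. The SUV gap.** Stable covers a fall below 15% and partial response starts at 25%. If only PMR and CMR count, a patient in the gap is a non-responder. If SMD counts too, the gap lies between two categories that both count. The yes/no result therefore rarely depends on it.

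**7. CT progression.** Section 6.5.1.2 rates one lesion, with PD at +25% of the longest diameter since treatment started. Appendix II rates the sum of diameters, with PD at +20% of the smallest sum. Examples with a single lesion:

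- 4.0 cm growing to 4.9 cm: 4.9/4.0 - 1 = +22.5%, which is SD under 6.5.1.2 and PD under Appendix II.
- 3.0 cm shrinking to 2.0 cm and regrowing to 3.0 cm: 3.0/3.0 - 1 = 0% against the longest diameter (SD), but 3.0/2.0 - 1 = +50% against the smallest (PD).

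**The case against.** The strongest reply is that the plan does point to a mapping. The Protocol Summary sets PET/CT against CT for judging local control, local control includes stable disease, and SD and SMD match by name. This stands in part. It makes stable disease on both sides the better-supported reading. A reader might infer from 6.5.1.5 that the plan sets a stable-inclusive CT rate against a PMR/CMR-only PET rate and so builds in a false difference. The documents do not say that; it is a possible reading and the less supported one. But the Protocol Summary item concerns local control, not the response rate being tested, and supplies no list of PET categories. The outcome is still undefined, and the favoured reading leads to the ceiling problem.

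A reader might also infer that one patient in the SUV gap could settle the test. That needs a strictly literal reading in which an unclassified fall counts as a failure even though SMD counts as success. The gap is a drafting fault with little effect on the result. The cited EORTC source may close it, but the protocol's own text does not.

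Counting stable disease as success is the plan's explicit choice, and the analysis is exploratory with at most 18 patients. Both points are fair. They argue for keeping the stable-inclusive rate under a clearer name and for a moderate severity. They do not excuse naming a test whose outcome is undefined on one side.

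**Conclusion.** The point holds as a defect of definition in one exploratory secondary comparison, plus a conflict in the CT progression rule that is wider. The absence of a PET responder rule and the single-scan stable-disease rule come directly from the text. The consequences are conditional. With stable disease on both sides, power is at most 1.9% for assumed rates of CT 95% and PET 85-95%. With it on CT only, the chance of a purely definitional difference is 0.13 at an assumed 20% stable share and 0.28 at 25%, and below 5% when the share is under about 16%. All of these assume 18 pairs and an exact two-sided 5% test.

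The conflict between 6.5.1.2 and Appendix II should not be read as confined to this comparison, because local control and local failure depend on the same progression call. Within the response rate it matters less: a patient stable or responding at any earlier first-year scan already counts. Nor do the documents support reading this as a threat to the trial's primary purpose; the MTD does not use these endpoints. The change should be made, at moderate priority.

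**What to change.** 1. **Response categories.** For the PET-versus-CT comparison, define response as CR, NCR or PR on CT and CMR or PMR on PET, as best response over the same first-year scans for both modalities. Label responses as unconfirmed where Appendix II's confirmation is not met. Keep the stable-inclusive rate of 6.5.1.5, reported on both modalities (SD with SMD), as a secondary disease control comparison in line with the Protocol Summary.
2. **Criteria.** Make the stable and partial-response cut-offs in 6.5.1.3 meet. Reconcile 6.5.1.2 with Appendix II so that one progression rule and one reference diameter apply to every CT endpoint.
3. **Paired set.** Use the patient as the unit. Restrict the paired comparison to FDG-avid patients with PET/CT at baseline and follow-up, and report how many are left out and why. Keep response rates in all eligible patients, as Appendix II requires.
4. **Reporting.** Give the paired 2x2 table and the difference with a 95% confidence interval (for example a Tango score interval), with the exact McNemar p-value as exploratory. For example, a 5-to-1 split in 18 pairs is a difference of (5 - 1)/18 = 22 points, interval -5.4 to 47.5, p = 0.22.

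**Cost.** No extra scans are needed, because the CT part of the PET/CT is of diagnostic quality (6.4.1). The endpoint for this one comparison changes. There will be fewer than 18 pairs, by a number the documents do not let us predict. Power does not rise: a nested 20-point difference in 18 pairs gives 13% whether the rates are 95% and 75% or 50% and 70%. What is gained is a comparison that can be interpreted.

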#### 6.5.1.6 Quality of life assessment

#### 6.5.1.6.1 Disease-specific information:

Disease specific information will be obtained by the data manager through the use of Electronic Data Interface for Transplantation (EDIT). EDIT is a computer application designed specifically for the Starzl Transplantation Institute at the University of Pittsburgh, which the LCC is affiliated. It provides the ability to track patients through the disease and treatment process. EDIT works in conjunction with other medical record systems that stores information regarding the patients' medical history (e.g., Medical Archive Record System). The data will be extracted from EDIT and summarized using Microsoft ACCESS 2000 and then transferred to SPSS.X for statistical analysis. Variables that will be extracted from EDIT will include: (1) stage of cancer, (2) tumor size, (3) lobar distribution of tumor, (4) suspected number of lesions, (5) grade of vascular invasion, (6) Child's-Pugh class, (7) presence of fibrosis or cirrhosis, (8) pathology of tumor, (9) capsulation of tumor, (10) ascites, (11) treatment type, (12) comorbid medical conditions, (13) medications; as well as lab values such as (14) prothrombin Time/Partial Thromboplastin Time PT/PTT), (15) electrolytes, (16) SGOT, (17) BUN, (18) SGPT, (19) creatinine, (20) LDH, (21) glucose, (22) alkaline phosphatase, (23) albumin, (24) total bilirubin. The disease-specific information will be analyzed to determine if there are baseline differences on any of these variables or contribute to a significant amount of the variance on any of the outcome variables (e.g., survival, disease progression, and HRQL). If any of the disease-specific variables are found to be different at baseline between the two treatment groups or are significantly related the outcomes at baseline, the variable will be covaried in later analyses.

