#### 7.0 Statistical Considerations

#### 7.1 Study Design/Endpoints

The primary objective of this study is to determine the Maximum Tolerated Dose (MTD) and safety of SBRT for liver metastasis using dose escalation. Dose escalation will be via the traditional "up and down" scheme indicated in the two tables below. The traditional up and down study design is a rule-based design which recruits up to 6 patients at each of the 3 dose levels. Patients in cohort(s) of 3 will be entered and the first cohort will be given the lowest dose. The detailed decision rule is in the two Tables below, where there are decisions corresponding to one or more dose limiting toxicities at any given dose level.

- The three dose levels are:
  - 50 Gy in 5 fractions (10 Gy/fx) delivered over a 2-week period.
  - 60 Gy in 5 fractions (12 Gy/fx) delivered over a 2-week period.
  - 75 Gy in 5 fractions (15 Gy/fx) delivered over a 2-week period.

Dose limiting toxicity (DLT) will be defined as any grade III stomach, bowel, liver, or spinal cord toxicity, or any grade IV toxicity as defined by the Radiation Therapy Oncology Group (RTOG). The monitoring and evaluation for dose escalation is referenced below in section 7.3.1. Cohorts of three patients each will be treated at a dose level. Only toxicities observed prior to 7 months after the last fraction of radiation will affect dose escalation.

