#### 7.2 Sample Size/Accrual Rate

The number of patients accrued to the study will depend on the MTD. No more than 18 evaluable patients will be treated in the trial. Based on previous efforts in recruiting patients at the University of Pittsburgh Cancer Institute, it is anticipated that at least 6 patients per year will be enrolled in the protocol and the accrual will be completed within 3 years. An evaluable patient is defined as one who either a) completes the five fractions and has no DLT until one month after the last fraction, or b) a patient who receives at least one fraction and suffers DLT. Patients who are not evaluable will be replaced.

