#### 7.3 Data Analysis

Data analysis will be done mostly by dose group and will be exploratory due to the small sample size.

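### The HRQL covariate rule names two treatment groups the trial does not have, and its significance-based selection from 24 variables would pick noise in at most 18 patients

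*Combined protocol and SAP*

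**What the plan says.** Section 6.5.1.6.1 lists the variables to be extracted from the clinical database. They are numbered to 24, ending with "22) alkaline phosphatase, (23) albumin, (24) total bilirubin", and one of them is the treatment itself: "10) ascites, (11) treatment type, (12) comorbid medical conditions". The section says the variables will be examined for baseline differences and for whether they "contribute to a significant amount of the variance on any of the outcome variables (e.g., survival, disease progression, and HRQL"). The next sentence sets the adjustment rule: if any variable is "different at baseline between the two treatment groups or are significantly related the outcomes at baseline, the variable will be covaried in later analyses". It gives no significance level, test, model or limit on the number of covariates.

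Section 7.1 describes a "rule-based design which recruits up to 6 patients at each of the 3 dose levels", and section 7.2 caps the trial: "No more than 18 evaluable patients will be treated in the trial". For the analysis as a whole, section 7.3 states: "Data analysis will be done mostly by dose group and will be exploratory due to the small sample size". For HRQL, section 7.3.2 states: "The HRQL data analysis will be mostly descriptive and performed according to Section 6.5.1.6".

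**The concern.** The rule reads like text written for a two-arm comparison. This trial gives one modality at 50, 60 or 75 Gy in 5 fractions and has no control or comparator. An analyst who follows section 6.5.1.6.1 must therefore first invent the two groups.

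The rule also lets significance tests choose the covariates, from a list that is longer than the number of patients. In a sample this small, a variable can be selected only if its observed association is large, and such associations arise easily by chance. The level, the test and the form of the model would all be settled after the data are seen. At stake is the credibility of any covariate-adjusted HRQL result, and HRQL is a stated secondary objective (section 2.4).

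**Working it through.** **Inputs from the documents.** There are 3 dose levels with up to 6 patients each (7.1), at most 18 evaluable patients (7.2), 24 listed variables (6.5.1.6.1), and the escalation and de-escalation tables in 7.1.

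**Assumption.** The screening level is not stated. I use 5% two-sided and show 10% as well.

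**The plan's own figure.** 3 × 6 = 18, which agrees with section 7.2. No HRQL sample-size or error-rate figure is stated, so there is none to reproduce.

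**Can each limb be run?**
- Difference between two treatment groups: no. Section 7.1 defines three dose levels, and section 7.3 analyses mostly by dose group. If escalation stopped early, two dose levels might be in use by chance, but the plan does not define that as the comparison.
- Relation to the outcomes at baseline: yes for HRQL, because FACT-Hep is collected before treatment (6.5.1.6.2, 6.6), once a level and a test are chosen. For survival and progression a baseline value does not exist.

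**Likely number of patients.** With no DLTs, the tables give 3 + 3 + 6 = 12. Simulating the tables with full cohorts gives a mean of 12.5 patients if the DLT rate is 5% at every level and 12.4 if it is 10%. Stopping accrual as soon as the second DLT occurs lowers the 10% figure to 12.2. About 12 to 13 is therefore more likely than 18.

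**Chance selection, for one outcome and 24 null variables.**
- Expected number selected: 24 × 0.05 = 1.2.
- At least one, if independent: 1 − 0.95^24 = 0.708.
- At least two, if independent: 1 − 0.95^24 − 24 × 0.05 × 0.95^23 = 0.339.
- At least one, at a 10% level: 1 − 0.90^24 = 0.920.
- With 22 usable variables: 1 − 0.95^22 = 0.677. This drops treatment type, and also vascular invasion, which inclusion criterion i restricts.

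**Allowing for correlation.** Independence is not realistic here. Child-Pugh class (item 6) is scored from ascites, bilirubin, albumin and prothrombin time (Appendix I), which are items 10, 24, 23 and 14. I simulated 24 equally correlated noise variables against a noise outcome at n = 18. The chance of at least one selection is about 60% to 62% at a pairwise correlation of 0.3 and about 47% at 0.5, with repeated runs differing by a point or so. The expected number stays close to 1.2.

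**What a selected noise variable looks like.** At n = 18, significance at 5% needs an absolute correlation of at least 0.47. At n = 12 it needs 0.58. Where at least one noise variable was selected and entered in a linear model for the same outcome, the mean R-squared was about 0.40 at n = 18 and 0.55 at n = 12. These values describe the outcome used for selection. They would carry over to later HRQL scores only as far as those scores follow the baseline score.

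**Precision of the replacement summary.** The half-width of a 95% CI for a mean paired change, in SD units, is t(0.975, n − 1)/√n:

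| n | Half-width (SD) |
|---|---|
| 3 | 4.303/1.732 = 2.48 |
| 6 | 2.571/2.449 = 1.05 |
| 12 | 2.201/3.464 = 0.64 |
| 18 | 2.110/4.243 = 0.50 |

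An interval within a dose level says almost nothing. One in all patients combined is usable.

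**The case against.** The strongest reply is that this is leftover wording of little consequence. HRQL is secondary, all analysis is labelled exploratory, the HRQL analysis is mostly descriptive, and no HRQL result enters the dose decisions. That stands as a limit on importance. It does not remove the rule: the sentence in section 7.3.2 that calls the analysis mostly descriptive also says it follows section 6.5.1.6, and the rule is worded as a commitment.

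A second reply is that 71% is too high. That also stands in part. The figure assumes independence and a level the plan never states, and correlation lowers it to about 47% to 62%. Exact tests on binary items would lower it further if the group limb were adapted to dose levels. At 3 v 3, the smallest two-sided Fisher p-value is 2/20 = 0.10, so nothing could be selected. The expected count of 1.2 applies to tests that hold their nominal size.

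A reader might also infer more than the documents support:
- **That the whole rule cannot be run.** Only the two-group limb cannot. The other works for baseline HRQL.
- **That variables are covaried because they predict survival or progression.** The preceding sentence examines those outcomes, but the trigger for covarying is a relation at baseline.
- **That a model with all 24 variables is planned.** Such a model could not be fitted: with three dose-group terms, 18 − 27 = −9 residual degrees of freedom. However, the plan covaries only the variables that are selected.
- **That adjusted estimates are the trial's only HRQL result.** Section 6.5.1.6.3 specifies subscale, FACT-G, total, Trial Outcome Index and symptom-index scores and lists minimally important differences. The unadjusted description is therefore the main output.

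**Conclusion.** The point holds. The first limb of the rule refers to a comparison that does not exist in this trial. The second can be applied only to baseline HRQL and would often select noise: about 1.2 of 24 null variables per outcome, with a chance of at least one between about 47% and 71%. These figures rest on an assumed 5% level, tests that hold that level, and pairwise correlations between 0 and 0.5. The MTD determination and the descriptive HRQL scores are not affected. Any covariate-adjusted HRQL result would be unreliable in a trial of about 12 to 18 patients. The text should be corrected, but this is not a threat to the primary objective.

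**What to change.** In section 6.5.1.6.1, delete the sentence on two treatment groups together with the significance-based covariate rule, and state that no covariate will be selected by test. The listed variables can still be tabulated.

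In section 7.3.2, state the HRQL analysis directly:
- Name one pre-treatment FACT-Hep assessment as baseline. Two are collected, at screening and at the first fraction.
- Summarise each patient's change from that baseline at each later time point, with a 95% CI for the mean paired change in all patients combined.
- Show individual values by dose level, without confidence intervals.
- Report the number of patients changing by at least a stated bound of each minimally important difference in section 6.5.1.6.3. These are given as ranges, such as 8 to 9 for FACT-Hep, so the lower or upper bound must be chosen in advance.

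The cost is protocol wording only. The assessments and the minimally important differences are already in the plan, so no new data or visits are needed.
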